At study closure, participants will also be asked to guess what study medication they were taking to assess the effectiveness of blinding, followed by a full debriefing regarding the study aims. All study participants will be financially compensated for study participation. Finally, one week and three months after the last treatment phase, participants will receive a follow-up phone call to determine if any side effects occurred as well as answer a pain history, the short form of the Brief Pain Inventory, the WOMAC, PANAS and the PSQI to inquire about pain and sleep respectively. During these calls, if symptoms that indicate imminent danger to the participant are reported such as dizziness, anxiety, drowsiness, balance problems, blurred vision, itchiness, irritation or stomach pain, staff will immediately advise participants to contact emergency medical services. Simultaneously, this matter will be immediately escalated to the study physician and PI and the physician or his proxy will be in immediate contact with the participant to determine appropriate steps for follow-up.

Subjects will participate in 4 separate sessions although to reduce participant burden additional sessions may be scheduled.

Sample essays: Blood samples will be collected from the subject's antecubital vein using a butterfly catheter and EDTA-coated lavender tubes (no more than 3 tbsp collected). The samples will be separated and aliquoted in [name] PAIN lab (Dental Tower). Assays will be performed in the Quest Diagnostics lab to evaluate standard clinical parameters (Comprehensive Metabolic Panel (CMP-14) while high sensitivity plasma GABA concentrations will be done using HPLC by Interdisciplinary Center for Biotechnology Research (ICBR) at UF.

Power and sample size considerations: For phase one, the estimated sample size was derived from the literature in sleep and pain studies assuming a medium effect size to achieve 80% power. For phase two of the study, we plan to recruit 28 participants, i.e., 14 participants in each of the randomly assigned treatment groups for the neuroimaging visits, this will provide effect sizes to determine the estimates of variability needed to calculate the sample size needed for future larger proposals working together with [name].

Data Analysis: [name] will work with the study team to perform data analytic procedures for both phases. For phase one, we will employ general linear model approaches to determine associations between pain and sleep measures while controlling for relevant covariates. For phase two we will employ a repeated pre-post analysis of variance to provide the basis for future estimations of effects including multiple comparisons corrections.

Recruitment Strategy: Recruitment of participants will be accomplished using newspapers and flyers, as well as community methods similar to our previous studies and social media advertisements on Facebook that direct the user to call a lab-controlled phone number. We will also contact individuals in the PRICE registry.

6. Possible Discomforts and Risks:

Equipment used in this research meets all current safety standards, and all research staff will be highly trained in the use of all equipment. This study may include risks that are unknown at this time. Potential risks for this study are related to using of study product, neuroimaging, blood draw procedure, blood pressure measurement, the physical performance tests, the cognitive function tests, the sensory testing, and potential loss of confidentiality related to study participation, as discussed in detail below.

All assessments will be conducted in [name] PAIN laboratory (Dental Tower) and the McKnight Brain Institute and all sessions will be conducted by trained and certified research staff, which will monitor potential adverse experiences and symptoms. During the testing sessions, a fully equipped defibrillator is available along with a semi-automated ECG cart. All personnel associated with the study have received CPR training and training on management of acute events including syncope, chest pain, acute dyspnea, focal neurological symptoms, and abnormal vital signs. Portable defibrillators are available at the assessment site. Additionally, a study physician is available on call and contact numbers for emergency services are posted. Institutional and community EMS services will be activated if needed. If participants develop chest pain, shortness of breath, or dizziness at any point during a screening or assessment visit, they will be instructed to rest and to contact the center and their physicians if these symptoms persist or recur.

Participants will be instructed to talk with the investigators about any discomforts that occur during the study. If for any reason the participant reports an injury, dizziness, anxiety, drowsiness, dry mouth, balance problems, constipation, blurred vision, itchiness, irritation or stomach pain, staff will immediately advise participants to contact emergency medical, they will be referred to their doctor, or the PI will call the doctor or other health care provider.

Before beginning data collection, all study coordinators undergo standardized training on all study procedures. A detailed checklist for each data collection element is in place to ensure all study coordinators are appropriately trained and able to conduct study procedures. Research coordinators will be certified in each element of the study visit including obtaining informed consent, administering questionnaires, protecting the confidentiality of collected data, performing the test batteries. Any study coordinator who is found to not adhere to all aspects of the protocol will be required to complete additional training followed by re-certification.

All research staff complete human subjects training required by The University of Florida institutional review board (IRB) and the National Institutes of Health (NIH). This training includes education about the importance of maintaining the confidentiality of personal health information. The study principal investigators or a co-investigator will be available to answer questions that arise during the informed consent process as needed. More information about specific protective measures against risk is outlined below.

GABA oral supplement administration

Gamma-aminobutyric acid (GABA) has become widely available as a food supplement. In the United States, GABA is considered a "food constituent" and a "dietary supplement," respectively. These GABA food supplements can be purchased online via numerous websites, including webshop giants such as Amazon.com, with often very positive customer reviews. Hundreds of people report that these supplements have helped them alleviate anxiety and/or improve sleep quality, in addition to other beneficial effects.

Physiological Effects of GABA. In recent years researchers have reported several placebo-controlled studies in which GABA was administered as a food supplement to healthy participants and participants with a history of acrophobia. One study found an increase in alpha waves in healthy participants and

increased levels of immunoglobulin A (IgA; an indicator of immune system functioning) in participants with a history of acrophobia when they were exposed to heights [50]. Another study reported reduced heart rate variability and salivary chromogranin A (CgA) during an arithmetic task compared to a control group after the administration of GABA-enriched chocolate [51]. Additionally, participants who received 50 mg of GABA dissolved in a beverage reported less psychological fatigue after completion of the task [52].

Safety of GABA oral supplement. No significant adverse events were reported in the above studies, indicating that GABA oral supplements are generally safe. Currently, there is no established dose for GABA as a dietary supplement, and doses in the literature range from 500 to 750 milligrams taken up to two times a day. As a precaution in our preliminary study, we decided to administer the lower dose of 500 mg daily.

Excluded Medical Conditions. As a precaution, we will exclude participants who take hypertension medications since GABA can reduce blood pressure levels. We will exclude participants that ingest neuropathic pain medication as well as anticonvulsants and antidepressants.

Drug-Interactions. It does not have any known drug interactions. However, we should know about any other medications or supplements participants are taking, including prescription drugs, nonprescription drugs, vitamins, and dietary or herbal supplements. Even though there are currently no known interactions, it is important to understand that gamma-aminobutyric acid supplementation has been studied very little in humans.

Placebo oral administration

This study compares an active drug (GABA) to a placebo. A placebo is an inactive substance made to look/taste like an active medicine.

Laboratory tests. Participants will have blood drawn at screening and during the post-intervention visit for both intervention periods to measure their blood chemistry. Abnormal results will be brought to the principal investigator's attention immediately. The results will be reviewed and signed by the study clinician and [name].

Assessment of Adverse Events. A standard operating procedure will be established which is followed to collect and deal with adverse events during the research project. In particular, adverse events will be systematically monitored both during the treatment phases, as well as 3 months following study completion. In particular, participants will respond to a side effect checklist to detect any possible physiological reactions related to the drug administration. This will include a series of open-ended questions asked by trained research staff regarding any adverse events that have occurred since the last visit or phone contact. Additionally, during the 3 months follow up, participants will be asked to the WOMAC PANAS and PSQI questionnaires to assess pain, feelings, and sleep respectively. This report will be reviewed by the principal investigator and study physician in a timely fashion. Any serious untoward event, whether related or unrelated to the study drug or procedures, will be reported to the UF IRB.

Adverse events will be defined as any physical symptoms or side effects that began following the administration of the study drug. All reported and observed adverse events will be tracked in a running adverse events participant log, which will contain information regarding dates, description, and severity. All adverse events will be coded using the most current version of the Medical Dictionary for Regulatory Activities (MedDRA). The number and percentage of participants reporting treatment-

emergent adverse events will be tabulated by treatment, system organ class, and MedDRA-preferred term. Treatment-emergent adverse events will be those adverse events that begin or worsened following the first dose of study drug. Adverse events will be further classified by severity and investigator-assigned relationship to study drug. All reported and observed adverse events will be tracked on a running adverse events log (specific to each subject and maintained in his/her study file) and will contain information regarding onset/offset dates, time course (i.e., single, sporadic), severity, action taken regarding study drug, relationship to study drug, and whether it meets FDA criteria for "Serious." Each reported event is reviewed by the principal investigator and the study physician in a timely fashion. Additionally, the principal investigator reviews all adverse events recorded in each participant's log after study participation.

In Case of Emergency. Participants will have 24-hour access to emergency care and will be provided with a means of contacting the on-call study doctor and research staff. Participants will be informed and encouraged to contact the study physician and study staff immediately with medical concerns or unusual reactions. Participants will also be informed of the closest Emergency Department location to their residence.

Data and Safety Monitoring Plan. A Data Safety Monitoring Plan will be in place. In particular, the following procedures will be implemented to ensure data and participant safety. Study progress and safety will be reviewed by the principal investigators in collaboration with a physician, and the study MD. We will stop the intervention if 30% or more of the participants in the GABA condition report seven or more (out of forty-four) of the side effects at moderate to severe levels over more than 3 days as acquired during the weekly check-in phone calls during the intervention phase. Data collected before the stop of intervention will be used for analysis. All participants who went through the intervention phase of the study will be followed up by phone calls for 7 days to ensure safety. Progress reports, including participant recruitment, retention/attrition, and adverse events will be provided to an Independent Safety Monitor for reviews on a bi-annual basis. The Independent Safety Monitor for this study will consist of an established senior investigator not associated with our study. A study end report will be compiled and will include a list and summary of adverse events. Also, this report will address: (1) whether adverse event rates are consistent with pre-study assumptions; (2) reason for dropouts from the study; (3) whether all participants met entry criteria; (4) whether continuation of the study is justified on the basis that additional data are needed to accomplish the stated aims of the study; and (5) conditions whereby the study might be terminated prematurely. The annual report will be signed by the Independent Safety Monitor and will be forwarded to the IRB, NIH, and FDA. The Data Safety Monitoring Plan will also require that all significant serious adverse events that may be possibly related to the study participants will be reported to the IRB, FDA, and NIH within 48 hours of the principal investigator's learning of the event. Besides, any unanticipated serious adverse events that may increase the risk of the research for participants or potential participants will be reported to the IRB and the NIH within 48 hours of the principal investigators being informed about the event. This study will be stopped before its completion if: (1) the intervention is associated with adverse effects that significantly impact the risk-benefit ratio, (2) study recruitment or retention becomes futile, (3) any new information becomes available during the trial that necessitates stopping the trial; or (4) if independent safety monitor indicates stopping trial is necessary due to adverse event frequency or severity.

ClinicalTrials.gov Requirements. Under Public Law 110-85 and NIH guidelines, the proposed research will be registered with ClinicalTrials.gov before the commencement of study procedures involving participants

Magnetic Resonance Imaging (MRI)/ Magnetic Resonance Spectroscopy (MRS)

MRI and MRS are used routinely for medical care and are very safe for most people, but participants will be monitored during the entire scan in case any problems occur. The risks of MRI/MRS are:

- The scanner contains a very strong magnet. Participants may not be able to have the MRI/MRS if they have any type of metal implanted in their body, for example, any pacing device (such as a heart pacer), any metal in their eyes, or certain types of heart valves or brain aneurysm clips. Therefore, participants will be extensively screened. Participants who would normally be excluded from getting an MRI/MRS for safety reasons will be excluded, applying criteria for an exclusion that are more stringent than those imposed for standard clinical MRI/MRS scans.
- There is not much room inside the scanner. Participants may be uncomfortable if they do not like to be in close spaces ("claustrophobia"). Participants will be screened for known claustrophobia.

The scanner produces a loud hammering noise, which has produced hearing loss in a very small number of people. Participants will be given earplugs to reduce this risk. Also, they will be informed of this possibility in the informed consent form and that they may immediately withdraw from the study at any time. During the procedure, participants will be able to talk with the staff through a speaker system, and, in the event of an emergency, participants can tell them to stop the scan.

During neuroimaging, participants will be situated comfortably on the scanner table, with a head-mounted. Brain image acquisition will take place on a 3T Siemens Prisma human imaging system at AMRIS, at the McKnight Brain Institute, employing pulse sequences and hardware that have been approved by the FDA for human clinical use. All MRI/MRS safety guidelines and precautionary steps established by the AMRIS will be strictly followed. At the end of the session, a post-scan debriefing questionnaire will be administered that examines discomfort during and after the scanning.

Blood Draw

The risks of drawing blood from a vein include discomfort at the site of puncture; possible bruising and swelling around the puncture site; rarely an infection; and, uncommonly, faintness from the procedure.

Blood Pressure Measurement

The risks of placing a blood pressure cuff on a participant's arms are that it may cause pinching or slight bruising.

Physical Tests

There is a risk of losing balance and falling or development of chest discomfort due to coronary ischemia or dyspnea due to heart failure or lung disease associated with the physical performance-based testing (e.g., the ¼ mile walk test, balance tests, rising from a chair). We will minimize this risk by: (1) safely escorting participants to chairs located along the walking course should they become unsteady; (2) following participants at a close distance; and, (3) being at participants' side should they need assistance. Research staff members will be trained in the conduct of the physical performance tests before they work with study participants. Study staff members are trained not to perform these tests if they feel that testing is unsafe. Besides, participants will be asked whether they feel the test is safe. Those who state it may be unsafe will not be allowed to complete the test. Staff members will be trained to protect against falling and will be trained in CPR. They will be trained in activating the emergency response system at the research facility.

Sensory Testing

The sensory testing procedures may be uncomfortable or unpleasant, in that participants may experience some temporary discomfort from the thermal, pressure, and mechanical stimulation. However, if the participants feel the sensation is greater than they wish to tolerate, they can stop any of the procedures at any time.

Personal Information

Some of the question's participants will be asked may be personal and may make participants feel uncomfortable. Time will be made to talk with the participant if they appear to be distressed. We will be asking for information about sensitive issues, such as mood which may make participants feel uncomfortable. If they are uncomfortable answering these questions, they can choose not to answer and discontinue participation in the study. Some people, when asked such questions, experience strong emotional reactions that may require counseling. If they do, they are strongly encouraged to tell the Principal Investigator, who can make an appropriate referral to the Psychology Clinic or the UF Counseling & Wellness Center at [contact]. If we should discover, based on the questionnaires or formal clinical interview, that the participant experiences marked depression or suffer from another psychiatric condition, we will offer to make an appropriate medical, psychiatric, and/or psychological referral.

Confidentiality

Data that will be collected from human subjects for this project will include behavioral performance measures, rating scales assessed through interviews and patients' responses to self-rated scales, physiological, and neuroimaging data. Data will be collected specifically for the proposed research project. Access to individually identifiable private information about human subjects will be limited to research staff affiliated with the project. Research records will be kept confidential to the extent provided by law. The collection and submission of medical information will be accomplished with strict adherence to professional standards of confidentiality. Participants' medical information will be kept in a secure location accessible only to research staff associated with this study. Participants will only be identifiable by ID number, and any published findings resulting from the study will not refer to or identify individuals. Several methods will be employed to maintain the confidentiality of participants. First, data will be collected in secure spaces where the session cannot be overheard. Secondly, only study investigators and key research staff (i.e. data manager and study programmers) will have access to the study database. Third, participants will be assigned a unique study identifier. Individual names are not linked with collected data in the password-protected study database and only the unique study identifier will be used. A file linking the participant name and contact information and their specific study identifier will be kept separately and will be password protected and only accessible to study team members. Fourth, collected data will be maintained in locked computer files and file cabinets to which only study team members have access. Collected data will be used only for research purposes. Published data will not contain any individual identifiers. Finally, all research staff members have to retake refresher course certification exams every year.

Informed Consent

Before entry in the trial, the investigator(s) or study coordinator(s) will explain to potential participants the aims, methods, reasonably anticipated benefits, and potential hazards of the trial and any discomfort it may entail. Subjects will be informed that their participation in the study is entirely voluntary and that they may withdraw consent to participate at any time. They will be told that competent physicians/lab personnel will examine their records but that personal information will be treated as strictly confidential and will not be publicly available. Subjects will be allowed to ask questions and will be given sufficient

time to review all of the relevant information associated with the study. After this explanation and before entry to the trial, the subject's consent will be obtained and documented via the signature of an informed consent form by both the subject and the person conducting the informed consent discussion. If signed informed consent cannot be obtained, the subject will not be included in the trial.

7. Possible Benefits:

There are no direct benefits for study participation. There may be benefits that we are not yet aware of. The report about the results of the study will be made available to study participants as well as others in the community. However, the greatest benefit will be to the society as a whole. Scientific knowledge advances slowly, but study results will increase our understanding of the underlying neurobiological mechanisms in sleep disorder and chronic pain in aging. Such knowledge may be implemented in intervention programs that may have the potential to increase function and personal well-being.

8. Conflict of Interest:

There are no conflicts of interest in this project.

References

- [1] J. L. Riley, C. D. King, F. Wong, R. B. Fillingim, and A. P. Mauderli, "Lack of endogenous modulation and reduced decay of prolonged heat pain in older adults," *Pain*, vol. 150, no. 1, pp. 153–160, Jul. 2010.
- [2] A. B. Neikrug and S. Ancoli-Israel, "Sleep disorders in the older adult - A mini-review," *Gerontology*, vol. 56, no. 2, pp. 181–189, 2010.
- [3] S. K. Roepke and S. Ancoli-Israel, "Sleep Disorders in the elderly," *Indian J Med Res* 131, 2010.
- [4] S. J. Enna and K. E. McCarson, "The Role of GABA in the Mediation and Perception of Pain," *Advances in Pharmacology*, vol. 54, pp. 1– 27, 2006.
- [5] M. [name], "Self-Care Wellness Toolkit Depression and Anxiety," 2015.

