We propose a double-blinded, randomized parallel group study that will randomize older adults with musculoskeletal pain and poor sleep quality to oral self-administration of either GABA (two 250mg capsules for a total of 500mg daily) or Placebo during four weeks. Our study design was guided by recommendations by the IMMPACT group for clinical pain trials [23][24][25][26] see table 1. After initial screening, eligible participants will undergo two 2.5-hour baseline sessions (health, sensory, and neuroimaging) for the collection of clinical information, QST, and brain imaging data. During the entire study, participants will wear a OURA ring to objectively measure sleep quality. During the intervention, participants will receive a phone call once a week for an assessment of adverse effects and compliance. During the last week of the intervention period, two assessment sessions will follow, these will be identical to the baseline sessions. (Figure 5.)

To reduce participant burden and exposure risk to COVID-19, the ICF may be conducted remotely via phone calls, UF Zoom and/or online (REDCap). A copy of the signed ICF will be provided to the participant.

Participants: Older adults over 45 years of age who have a smartphone and have experienced pain of at least moderate intensity (>5/10 pain intensity ratings) on more days than not during the past three months, and who also reported poor sleep quality (>5 PSQI scores) will be considered for participation. Community-based recruitment methods established in [name] lab will be utilized.

Exclusion criteria will align with study and safety requirements broadly related to GABA administration, pain and MRI : 1) serious psychiatric conditions (e.g., schizophrenia, major depression, bipolar disorder;

Table 1. Study measures consistent with core outcome domains recommended by IMMPACT- www.immpact.org

IMMPACT Core Outcome Domain	Proposed Study Measures
Pain	Verbal Descriptor Scale (VDS) WOMAC-Pain
Physical functioning	WOMAC-Physical Function
Socio-emotional functioning	BDI-II PANAS
Sleep	Pittsburgh Sleep Quality Index Berlin Questionnaire Epworth Sleepiness Scale OurA Ring Sleep Diary
Improvement and satisfaction with treatment	Multidimensional Patient Impression of Change

Symptoms and adverse events	Passive capture of spontaneously reported adverse events and symptoms, with the use of open-ended prompts

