Initial screening: Interested individuals will call in using the provided phone number and after the phone consent that provides the individual information about the study and if they are interested, a pre-screening will be conducted. This screening procedure will include two questions regarding general body pain, two questions regarding back pain and seven questions regarding sleep quality in the past month. Will also assess age, gender, and additional health history information, as well as a questionnaire to assess MRI eligibility. After the phone pre-screening, if participants are eligible and still interested in participation, the baseline orientation visit will be scheduled. **Baseline Health & Sensory Assessment**

Session: After receipt the signed copy of the informed consent previously obtained using REDCap, participants will provide a fasting blood sample to evaluate standard clinical parameters (Comprehensive Metabolic Panel (CMP-14) Blood Test) and a Urine sample to measure urine specific gravity, which will be reviewed by a physician to determine study continuation. For women under the age of 62, pregnancy tests will also be conducted. This session will take place in the mornings to accommodate for fasting and to control for circadian fluctuations.

Physical examination. Height and weight will be measured as well as vital signs. Participants will complete a thorough Medical and Pain History Questionnaire, including a review of bodily systems assessing the reported duration of their pain, comorbid conditions, and current medication use.

Figure 5. Study Procedures

Sleep quality will be assessed with the Pittsburgh Sleep Quality Index (PSQI) [39] and PSQI total score will be our primary sleep outcome measure. Secondary sleep measures include Berlin Questionnaire[40], Epworth Sleepiness Scale[41], PROMIS-Sleep Related Impairment Short Form 8a[47], and FOSQ-10: A Short Version of the Functional Outcomes of Sleep Questionnaire [48].

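### Phase 2 should compare the arms by ANCOVA on the baseline already collected; the planned pre-post ANOVA is valid but usually less precise at 14 per arm

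*Combined protocol and SAP*

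**What the plan says.** All references are to section 5 (Research Plan) of the combined protocol and SAP unless noted.

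- **Design.** The Second Phase opens: "We propose a double-blinded, randomized parallel group study". Power and sample size considerations gives the size: "we plan to recruit 28 participants, i.e., 14 participants in each of the randomly assigned treatment groups".
- **Measurements.** After baseline, in the last treatment week, "two assessment sessions will follow, these will be identical to the baseline sessions". Every Phase 2 outcome therefore has a baseline value.
- **Analysis.** One sentence: "For phase two we will employ a repeated pre-post analysis of variance to provide the basis for future estimations" of effects, with a correction for multiplicity. The sentence before it provides for covariates, but for Phase 1 only. Nothing elsewhere adds baseline adjustment to Phase 2, and no contrast is named as the test of treatment.
- **Purpose.** Of the 28 participants, Power and sample size considerations says "this will provide effect sizes to determine the estimates of variability needed to calculate the sample size needed for future larger proposals".
- **Entry criteria.** Pain above 5/10 is required, from people "who also reported poor sleep quality (>5 PSQI scores) will be considered for participation". PSQI total and self-reported pain intensity (Verbal Descriptor Scale, VDS) are also the primary sleep and pain outcomes. The phone screen includes "two questions regarding back pain and seven questions regarding sleep quality in the past month"; the plan does not say whether the entry score is the baseline that will be analysed.

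**The concern.** Hypotheses H2a to H2d and H3a to H3b (Specific Aims) are all comparisons of GABA with placebo, and all rest on that one sentence. A change score fixes the coefficient on baseline at 1. ANCOVA estimates it, and so uses the baseline more efficiently whenever the pre-post correlation is not very high. With 14 per arm, intervals wider than they need to be make the effect estimates less informative.

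The second consequence concerns later trials. The plan does not say which SD will be carried forward. If a later trial is analysed by ANCOVA but sized from the change-score SD, its sample size will be overstated. If it too uses change scores, the change-score SD is the right input.

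**Working it through.** **Inputs.** From the documents: two randomised parallel arms, 14 + 14 = 28 participants, one baseline and one post-intervention value per outcome. Phase 2 has no stated alpha, power, effect size or SD, so there is no sample-size calculation to reproduce. Assumed: pre-post correlation ρ of 0.3 to 0.9; equal pre and post SDs (σ = 1); complete data; and, for power only, a two-sided alpha of 0.05 and a true difference of 0.8 SD.

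**Step 1: what the planned test is.** In a two-arm, two-time-point ANOVA the group-by-time F on (1, 26) df equals the square of the change-score t. In a numerical check the two agreed (5.4773 and 5.4773).

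**Step 2: variances.**
- Change score: 2(1 − ρ)σ², 26 df, critical t 2.056.
- ANCOVA: (1 − ρ²)σ² × (N − 3)/(N − 4) = (1 − ρ²)σ² × 25/24, 25 df, critical t 2.060. The factor 25/24 is the price of estimating the slope.
- Ratio, ANCOVA to change: (1 + ρ)/2 × 25/24. It equals 1 at ρ = 2 × 24/25 − 1 = 0.92.

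**Step 3: results.** Equivalent N is 28 divided by the ratio. Half-widths are means over 40,000 simulated trials per setting. Power is from the noncentral t.

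| ρ | Change variance | ANCOVA variance | Ratio | Equivalent N | 95% CI half-width (SD) | Power at 0.8 SD |
|---|---|---|---|---|---|---|
| 0.3 | 1.40 | 0.948 | 0.677 | 41.4 | 0.91 → 0.75 | 0.406 → 0.552 |
| 0.5 | 1.00 | 0.781 | 0.781 | 35.8 | 0.77 → 0.68 | 0.531 → 0.634 |
| 0.7 | 0.60 | 0.531 | 0.885 | 31.6 | 0.60 → 0.56 | 0.749 → 0.797 |
| 0.9 | 0.20 | 0.198 | 0.990 | 28.3 | – | 0.995 → 0.995 |

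Simulation gave ratios of 0.681, 0.774, 0.885 and 0.991, bias within 0.003 SD for both methods, and type I error of about 5% for both.

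**Step 4: PSQI and pain, if entry truncates the analysed baseline.** Suppose a normal baseline is cut at its mean. Its variance falls to 1 − 2/π = 0.363. The change-score variance becomes (1 − ρ)² × 0.363 + (1 − ρ²), while ANCOVA stays at (1 − ρ²) × 25/24. At ρ = 0.5 that is 0.091 + 0.75 = 0.841 against 0.781, a ratio of 0.93. Simulated ratios at underlying ρ of 0.3, 0.5, 0.7 and 0.9 were 0.876, 0.924, 0.977 and 1.021. Power moved from 0.499 to 0.553, from 0.602 to 0.633 and from 0.791 to 0.795 at the first three. Ring sleep measures, quantitative sensory testing (QST), brain GABA and plasma GABA are not entry criteria, so Step 3 is the relevant table for them.

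**Step 5: the later trial.** Sizing an ANCOVA trial from the change-score SD inflates N by 2(1 − ρ)/(1 − ρ²) = 2/(1 + ρ), which is 1.54, 1.33 and 1.18 at ρ of 0.3, 0.5 and 0.7. For scale, a variance estimated on 26 df has a 95% range of 26/χ², about 0.62 to 1.88 times the estimate.

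**The case against.** The planned analysis is valid, and this is a 28-person pilot with no power target to miss. Choosing between two valid methods could be called a matter of taste.

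Several narrower points carry weight:

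- **The 0.92 break-even needs equal SDs.** With the baseline cut at its mean, break-even drops to an underlying ρ of about 0.80, an observed pre-post correlation of about 0.63. For the two primary outcomes the gain may be small, or a slight loss. This stands, though the degree of truncation is itself unknown.
- **The planning inputs are not destroyed.** The ANOVA's two error mean squares estimate σ²(1 + ρ) and σ²(1 − ρ). Under equal SDs these yield σ and ρ. This stands too, but only if both are reported, which the plan does not promise. The inflation in Step 5 is also smaller than the sampling error of the variance; unlike that error, it is systematic and avoidable.
- **Power at an uncorrected 0.05 is not this trial's power,** since a multiplicity correction is planned. True; the power figures only illustrate the contrast between methods.
- **The plan never says that group-by-time is the test.** True, and a reason to rewrite the sentence. If the group main effect were read instead, it would average pre and post and halve the effect: simulated power at ρ = 0.5 is 22%, against 53% for change scores and 63% for ANCOVA.

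None of this makes ANCOVA a poor choice. In these calculations its variance penalty is at most about 4% (25/24 = 1.042, as ρ approaches 1), against gains of 11% to 32% in the middle of the range for outcomes not used for entry.

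**Conclusion.** The point holds, as a recommended improvement and not as an error of validity. Both analyses estimate the same treatment effect without bias and keep the type I error near 5%. For outcomes not used for entry, ANCOVA is more precise below a correlation of about 0.92: variance falls by about 32%, 22% and 11% at ρ of 0.3, 0.5 and 0.7, and by about 1% at 0.9. For PSQI and pain under the assumed truncation the figures are about 12%, 8% and 2%, with a loss of about 2% at 0.9.

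The direction is well supported. The size is not fixed by the documents: it depends on ρ, on the pre and post SDs, on a linear relation with no arm-by-baseline interaction, and on all 28 participants giving both values. The overstatement of a later trial's N arises only if that trial uses ANCOVA and is sized from the change-score SD.

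**What to change.** Replace the Phase 2 sentence in Data Analysis with, for example:

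> For phase two, each continuous outcome (PSQI total, VDS pain intensity, ring sleep measures, QST measures, brain GABA, plasma GABA) will be analysed by ANCOVA, with the post-intervention value as outcome, treatment arm as factor and the baseline value of the same outcome as covariate. The adjusted difference between arms will be reported with its 95% CI, applying the planned correction for multiplicity. As planning inputs for later trials we will report the residual SD, the baseline and follow-up SDs and the pre-post correlation.

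This names the treatment contrast and gives a later team what it needs to size either analysis. It should be fixed before Phase 2 data are unblinded. The plan should also state which PSQI and pain scores serve as the analysed baseline.

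The cost is one replaced passage and one residual degree of freedom (25 instead of 26). No new data or visits are needed.
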